10.3 Statistical Plan Deviations

Any deviations to the statistical plan will be described and justified in updated versions of the protocol and in the final report, as appropriate.

10.4 Selection of Participants for Analyses

All infants recruited in the study will be evaluated statistically provided the participant is not withdrawn from the study before discharge from the hospital, and parents are satisfied for us to use the data.

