6.4 Participant Withdrawal Criteria

Participants may be withdrawn from the study at any time if requested by one or both parents. Participants may be withdrawn from the study by attending physicians if they develop a complication that may be reasonably attributed to the study. The reason for withdrawal will be documented. No further data will be obtained from the withdrawn infant, regardless of whether the infant still requires care in the NICU at any study site. Data obtained up until the point of withdrawal will still be used for data analysis.

Withdrawn participants will not be replaced by further recruitment of an infant for the respective age group.

7 Treatment of Participants

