10.1 Statistics and Interim Analysis

Data will be analysed in R software (open-source) on an intention to treat basis by the trial biostatistician ([name]) and performed blinded to study group assignment.

Missing data will be handled via multiple imputation.

Children unable to be tested on Bayley-4 due to death, disability, severe delay or performance below threshold for individual composite scores will be assigned a score of 49.

Comparability of study groups at baseline will be based on patient demographic data (birth weight Z-score, gestation, exposure to chorioamnionitis and maternal steroids, maternal shift work) and baseline physiological circadian rhythmicity determined at randomisation.

Descriptive statistics will include mean (SD), median (IQR) for continuous variables with symmetric and asymmetric distributions, respectively, and counts/percentages for categorical variables.

Cognitive scores between the two groups at 2 years cPNA (primary outcome) will be analysed using (1°) ttest and (2°) linear mixed effects regression, adjusted for socioeconomic status, parental risk index, sex, birthweight Z score, gestation age, antenatal and postnatal steroid use, key neonatal morbidity count and including random effects for multiple birth ID and site. The false discovery rate employed for all secondary analyses will use the Benjamini-Hochberg algorithm.

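### Section 10.4 leaves infants withdrawn before discharge out of the analysis, contradicting intention to treat in 10.1 and the use of data up to withdrawal in 6.4; the exclusion can differ by arm

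*Protocol*

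**What the plan says.** Section 10.4 is the only place where the protocol says which infants are analysed: "All infants recruited in the study will be evaluated statistically provided the participant is not withdrawn from the study before discharge from the hospital". A second condition, joined by a conjunction, follows: "and parents are satisfied for us to use the data".

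Section 10.1 gives the analysis principle: "Data will be analysed in R software (open-source) on an intention to treat basis". It plans multiple imputation for missing data and assigns a score of 49 to children who cannot be tested because of death, disability or severe delay.

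Section 6.4 gives two routes out of the study. One is parental: "Participants may be withdrawn from the study at any time if requested by one or both parents". The other is medical: "Participants may be withdrawn from the study by attending physicians if they develop a complication that may be reasonably attributed to the study". For both routes it then says "No further data will be obtained from the withdrawn infant", and also "Data obtained up until the point of withdrawal will still be used for data analysis".

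Four other sections bear on the point:
- Section 13.1 keeps the interventions out of use outside the intervention arm.
- Section 5.3 says that families and care staff cannot be blinded.
- Section 7.2 allows eye-masks to be stopped, for a time or for good, while the infant stays in the trial and the other components continue.
- Sections 9.2.1 and 9.2.2 list device-related adverse events and send all adverse events to the ethics committee and the DSMC.

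**The concern.** An infant withdrawn before discharge is out of the analysis under 10.4, in it up to withdrawal under 6.4, and in it under the assigned arm under 10.1. No per-protocol or secondary set is named to which 10.4 might be meant to apply. Unless this is settled beforehand, the primary population will be chosen once the data are in.

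Following 10.4 would drop infants because of something that happened after randomisation. One route to withdrawal is a complication attributed to the study, judged by staff who know the allocation, in a trial where one arm alone receives the devices as study treatment. If such withdrawals are more common in that arm, and if those infants would have scored differently from the rest, the two analysed groups are no longer the groups that were randomised. The same infants would also be missing from the final between-arm comparison of safety outcomes.

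The end of data collection in 6.4 adds to this. An infant withdrawn by a physician has no 2-year Bayley-4 score even where the parents would gladly attend.

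**Working it through.** **The rules side by side, for an infant withdrawn before discharge whose parents allow use of the data**

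| Section | Is the infant analysed? | Is a 2-year score obtained? |
|---|---|---|
| 10.1 | Yes, in the assigned arm; missing values imputed | Not addressed |
| 6.4 | Yes, with data up to withdrawal | No |
| 10.4 | No | Not applicable |

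The parental condition in 10.4 does not resolve this. It is an additional requirement and does not limit the exclusion to families who refuse use of their data.

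**The plan's own figure.** For a 4-point difference, SD 15, two-sided 5% and 90% power, the t-test needs 296.5, so 297 per group and 594 in total. Section 10.2 rounds this to 600. Then 600 / 0.7 / 0.9 = 952.4, taken to 954, or 477 per arm. The sample size reproduces and is not in dispute; it serves here only as a denominator.

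**Illustration of size.** Let w be the share of an arm excluded, and D the mean deficit of the excluded infants against the retained infants of the same arm, whose mean is m.
- Mean of the full arm: (1 − w)m + w(m − D) = m − wD.
- Mean after exclusion: m.
- Shift in that arm: wD.
- Shift in the difference between arms: w₁D₁ − w₀D₀, with 1 for intervention and 0 for control.

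The protocol gives neither w nor D, so the following are assumptions. Take D₁ = 10 points and no exclusions in controls (w₀ = 0):
- w₁ = 2% (0.02 × 477 = 9.5 infants): 0.02 × 10 = 0.2 points, 5% of the 4-point target.
- w₁ = 5% (23.9 infants): 0.05 × 10 = 0.5 points, 12.5% of the target.
- w₁ = 8% (38.2 infants): 0.08 × 10 = 0.8 points, 20% of the target.

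If the two arms lost the same share with the same deficit, the terms would cancel and the shift would be zero. If the control term were larger, the sign would reverse.

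**Effect on the false-positive rate.** With no true effect, 300 per arm and SD 15, the standard error is 15 × √(2/300) = 1.22. A shift of 0.5 points raises the two-sided rejection rate from 5% to 6.9%.

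**Which section causes the shift.** Under 6.4 these infants have no 2-year score however 10.4 is read. If 10.4 alone is corrected, their scores are imputed. If imputation recovers a fraction f of the deficit, a shift of wD(1 − f) remains. It disappears only if the data collected before withdrawal fully explain the deficit (f = 1). The illustrated shift therefore depends largely on the end of data collection in 6.4, and both sections need to change.

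**The case against.** The strongest reply accepts the contradiction but questions what is built on it. A reader might infer three stronger claims, and the documents support none of them.

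*That the exclusion is differential by arm.* Section 6.4 names parental request first, and that route is open in both arms. The physician route refers to the study as a whole, which includes sub-study swabs and actimeters and fixed medication times in both arms. Controls may also wear eye-masks for phototherapy and ear protection during high-frequency ventilation. Section 7.2 lets eye-masks stop without withdrawal, which should keep physician withdrawals few. What stands is that the exclusion can be differential: the devices are study treatment in one arm, and those attributing complications are unblinded.

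*That device harm is hidden.* Skin damage and perceived device safety problems are listed adverse events. They are recorded prospectively and reported to the DSMC and the ethics committee, and a complication that prompts withdrawal precedes it. Safety surveillance is therefore intact. Only the final statistical comparison between arms could lose these infants.

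*That the bias is large.* A 20-point gap would give 0.4 to 1.6 points at the same 2% and 8%, but 20 points is 1.33 SD. The protocol does not link skin, eye or ear problems to a cognitive deficit of that order, or of 10 points. Deaths are scored 49 and are not called withdrawals, so the worst outcomes are not shown to be dropped.

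An SAP that was not available here might define the set differently. That would not answer the point, because 10.4 states a rule and does not leave the matter open.

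**Conclusion.** The contradiction is certain: 10.4 conflicts with 10.1 and with 6.4, and the protocol contains nothing to reconcile them. Followed as written, 10.4 makes an exclusion after randomisation that is not intention to treat.

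That the exclusion can differ by arm is a reasonable inference from the design. That it will do so, and that it would favour the intervention, is not established. The 0.2 to 0.8 points are illustrative. They rest on an assumed withdrawal share of 2% to 8%, an assumed 10-point deficit and no matching exclusions in controls, and they arise largely from the end of data collection in 6.4 rather than from 10.4 alone. The actual bias could be negligible.

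The point should still be corrected, because it decides the primary analysis population and is cheap to settle before the unblinded analysis.

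**What to change.** Reconcile sections 6.4, 10.1 and 10.4.

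- **Analysis set (10.4, consistent with 10.1).** The primary set is all randomised infants in their assigned arm. Infants withdrawn before discharge remain in it, with data up to withdrawal used and later values imputed. The only exception is where parents refuse use of the data, and these infants are counted and reported by arm.
- **Data collection (6.4).** Only parental withdrawal of consent ends data collection. Infants withdrawn by a physician are followed to the 2-year Bayley-4 where the parents agree.

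The cost is a wording amendment and the follow-up of a few more infants. The sample size of 954 is unchanged, and no clinical rule on use or discontinuation of the devices is altered.

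### Section 10.4 leaves infants withdrawn before discharge out of the analysis, contradicting intention to treat with imputation (10.1) and the use of data up to withdrawal (6.4)

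*Protocol*

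**What the plan says.** Three places in the protocol bear on who is analysed.

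- **Section 10.4**, the section devoted to selecting participants for analysis: "All infants recruited in the study will be evaluated statistically provided the participant is not withdrawn from the study before discharge from the hospital". It adds a second condition, that parents agree to use of the data.
- **Section 10.1**: "Data will be analysed in R software (open-source) on an intention to treat basis", and "Missing data will be handled via multiple imputation".
- **Section 6.4**: "Data obtained up until the point of withdrawal will still be used for data analysis". The same section says "No further data will be obtained from the withdrawn infant", and makes clear that this covers infants who are still in intensive care. Withdrawn infants are not replaced.

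Section 6.4 gives two routes to withdrawal. One is parental: "Participants may be withdrawn from the study at any time if requested by one or both parents". The other is medical: "Participants may be withdrawn from the study by attending physicians if they develop a complication that may be reasonably attributed to the study". Section 5.3 says that families and treating staff cannot be blinded. Section 5.5 runs the intervention from birth to discharge home.

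**The concern.** An infant withdrawn in the NICU is dropped under 10.4, retained in the assigned arm under 10.1, and retained with data to date under 6.4. An analyst could cite the protocol for either analysis set. If that choice is made after allocation is known, the primary result is open to challenge.

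The exclusion in 10.4 acts after randomisation and covers the period in which the intervention is given. The people who can trigger it know the allocation, and one stated trigger is a complication attributed to the study. The excluded infants may therefore differ between arms in number and in prognosis, and the Bayley-4 comparison would become one of infants who stayed in the study. The rule also takes these infants' pre-withdrawal neonatal outcomes out of the final between-arm comparison, although 6.4 says those data are to be used.

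**Working it through.** **Step 1. Can the three sections be reconciled?**

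| Infant withdrawn before discharge | 10.4 | 10.1 | 6.4 |
|---|---|---|---|
| In the analysis set? | No | Yes, as randomised | Yes, with data to date |
| Data before withdrawal | Not evaluated | Used | Used |
| Missing 2-year score | Does not arise | Imputed | Not collected |

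Two readings might remove the conflict, and neither works. Section 6.4 cannot be confined to withdrawals after discharge, because it expressly covers infants still in the NICU. Section 10.4 is not only a consent clause, because its two conditions are joined by *and*: an infant withdrawn before discharge is left out even when the parents agree to use of the data.

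**Step 2. The plan's own figure.** Section 10.2 uses a 4-point difference, SD 15, two-sided 5% and 90% power. The t-based solution is 296.5 per group, rounded up to 297 as stated. Then 600/0.7/0.9 = 952.4, against 952.3 in the text and a final 954. The figure reproduces and is not in dispute.

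**Step 3. Loss of power.** With the protocol's own factors, 954 × 0.7 × 0.9 / 2 = 300.5 effective infants per arm. Excluding a further 2%, 5% or 10% of both arms gives power of about 89.9%, 89.0% or 87.3%. This is a minor effect.

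**Step 4. Gross bias.** The protocol gives neither the share withdrawn nor their score deficit, so both are assumptions. Let w be the share excluded, in the intervention arm only, and d the deficit of those infants relative to the infants retained. The intervention mean is then overstated by w × d.

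| w | d = 5 | d = 10 | d = 15 |
|---|---|---|---|
| 2% | 0.10 | 0.20 | 0.30 |
| 5% | 0.25 | 0.50 | 0.75 |
| 10% | 0.50 | 1.00 | 1.50 |

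Against the 4-point target this runs from 0.1/4 = 2.5% to 1.5/4 = 37.5%.

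**Step 5. Chance of a false claim of benefit** (nominal 2.5% in that direction). Use P = 1 − Φ(1.96 − bias/SE), with SE = 15 × √(1/[n(1 − w)] + 1/[n(1 − w_c)]), where w_c is the share of controls excluded and the bias is (w − w_c) × d. For n, take 477 × 0.9 = 429.3 per arm (siblings treated as independent) or 300.5 (with the protocol's 0.7 factor).

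| w, d | n = 429.3, no controls excluded | n = 300.5, no controls excluded | n = 429.3, controls excluded at half the rate |
|---|---|---|---|
| 3%, 5 | 3.5% | 3.3% | 3.0% |
| 5%, 10 | 7.0% | 6.0% | 4.3% |
| 10%, 10 | 15.6% | 12.2% | 6.8% |
| 10%, 15 | 29.7% | 22.2% | 10.5% |

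For example, w = 10% and d = 10 with no controls excluded give SE = 1.052 at n = 429.3, so P = 1 − Φ(1.96 − 0.951) = 15.6%. The last column assumes the same deficit in both arms.

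**The case against.** The contradiction itself has no good answer. The case on the other side is about how much follows from it, and most of that case stands.

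- **Link to arm.** A reader might infer that withdrawals for complications will fall almost only in the intervention arm. The protocol does not establish this. Section 6.4 speaks of complications attributed to the study, not to the devices. Both arms have study-imposed medication timing (7.1.2), and section 9.2.1 lists necrotising enterocolitis and retinopathy as study-related events without reference to arm. Section 7.2 lets eye-masks be stopped for a skin, eye or ear condition without withdrawing the infant, so those infants stay in the analysis. Parents may withdraw from either arm. A difference by arm is plausible, but its size and direction are not documented.
- **Prognosis.** Infants not expected to survive are excluded at entry (6.3), and death or untestable disability is scored 49 (10.1) and is not a withdrawal. A large deficit among withdrawn infants is therefore an assumption.
- **Safety.** A reader might infer that 10.4 erases the harm record. It does not. Section 9.2.2 has all adverse events documented prospectively and reported to the ethics committee and the DSMC, with no condition from 10.4. What is lost is these infants' contribution to the final comparison. Deaths after withdrawal go unrecorded because 6.4 stops data collection, and rewording 10.4 would not recover them.
- **Size attributable to 10.4.** Because 6.4 leaves the 2-year score missing under either rule, w × d is the gross bias and not the gain from correcting 10.4. Imputation removes only the part that baseline and pre-withdrawal data predict.

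None of this tells the analyst which of the three rules to follow.

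**Conclusion.** The point holds as a contradiction in the definition of the analysis set, and it must be resolved before anyone sees data by arm. The rule in 10.4 is a post-randomisation exclusion in an open-label trial and is incompatible with 10.1 and 6.4.

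The size of any bias is unknown. The range of 0.1 to 1.5 points is a ceiling for each assumed pair of values: exclusion of 2% to 10% in the intervention arm only, with a deficit of 5 to 15 points. It shrinks if controls also withdraw, and at the low end it is negligible. The documents do not show that the result would be biased towards the intervention, or that safety events would go unreported. The ground for the change is that the protocol gives conflicting instructions on who enters the primary comparison.

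**What to change.** Replace section 10.4 with wording such as:

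> All randomised infants are analysed in the arm assigned. Data up to withdrawal are used, and missing Bayley-4 scores are handled by multiple imputation using baseline and pre-withdrawal data. The only data removed are those for which a parent explicitly revokes permission for use; their number and the reason are reported by arm.

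This agrees with 10.1 and 6.4 and keeps the consent condition already in 10.4. The set without withdrawn infants may be kept as a sensitivity analysis only. The cost is one paragraph of protocol text, with no extra infants or visits and no change to the sample size of 954.

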10.5 Data Management

De-identified study data will be collected and entered into a secure online study database using REDCap (Research Electronic Database Capture) provided by the Biometrics team at the Telethon Kids Institute, hosted on Telethon Kids Institute infrastructure within the Perth Children's Hospital. REDCap has inbuilt capacity for eligibility confirmation, 24/7 randomisation/allocation within multi-stratified trial designs, and scheduling of follow-up, including timed survey distribution to participant families.

Randomisation tables will be generated by the trial biostatistician. We will use developed instruments for automatic de-identified import of routine pregnancy, birth, demographic and care during initial hospitalisation coded by the Australian New Zealand Neonatal Network. Additional study specific data fields will be collected and entered into the database prospectively.

Data collected will include primary and secondary outcomes, patient demographics (birth weight Z-score, gestation, exposure to chorioamnionitis and maternal steroids, maternal shift work) and postnatal confounders (e.g. duration of mechanical ventilation, exposure to therapeutic postnatal steroids, and episodes of confirmed sepsis (blood culture positive)).

10.6 Procedures for Missing, Unused and Spurious Data

Missing values will be imputed as appropriate and in consultation with a biostatistician. Data will be reviewed prior to analysis for extreme outliers and where reasonable these data will be removed from the analyses. All samples collected will otherwise be used in the study.

11 Monitoring / Audit

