3.1 Background Summary

Prematurity (birth before 37 completed weeks gestation) is one of the most pressing health problems: globally, preterm birth accounts for more than 10 % of births and over 1.1 million neonatal deaths annually.¹ Cognitive impairment is the major and most distressing disability arising from preterm birth and the primary concern for parents and carers of preterm infants after hospital discharge. Cognitive impairment reflects the vulnerability of the preterm brain to disrupted development: children born preterm perform at >0.8 SD below term peers on IQ tests.² Premature babies also exhibit higher rates of adverse motor, behavioural and psychiatric outcomes in late childhood compared to children born at term gestation, even in the absence of recognised perinatal brain injury.³ Such life-long neurological deficits have enduring health and socio-economic consequences for these fragile infants, their family, and society. Rates of cognitive impairment after preterm birth have not improved in recent decades despite improved survival.^{4,5}

Circadian rhythmicity is essential to neurogenesis, learning, memory, and thus vital to development of normal cognition, as well as the structural and function integrity of developing organs.⁶

Circadian rhythmicity in circulating melatonin promotes onset of sleep at night when melatonin peaks, whereas peaking of the circulating cortisol levels in the early morning promotes wakefulness. The fetus is dependent on maternal circadian physiological cues (e.g. temperature; melatonin and cortisol) to orchestrate developmental processes until near term.^{7,8} Maternal circadian rhythm disruption (e.g. shift work), decreases fetal growth.⁹ Restricted fetal growth impedes short- and long-term fetal brain development and brain function (including intellectual, behavioural and motor functioning).^{10,11} In contrast, maternal melatonin improves neurodevelopment in the growth-restricted fetus.¹² Melatonin is neuroprotective for the developing brain: melatonin reduces inflammation, oxidative stress, lipid peroxidation, and cell death, and stabilises the blood-brain barrier after fetal asphyxia.¹³⁻¹⁶ Early endogenous production of this hormone thus has scientific credibility for improving neurodevelopmental outcomes. Rhythmic release of glucocorticoids are similarly vital for regulation of neural cell differentiation and death.¹⁷

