5.1 Study Endpoints

- 5.1.1 Primary outcome
 - Cognitive scores on the Bayley-4 around 2 years cPNA⁴⁶

The Bayley-4 is an individually administered instrument to assess developmental functioning in infants and young children from the age of 1 month to 42 months of age. The Bayley-4 is the current, universal national test of early development. The Bayley-4 sub-scores include cognitive, language (composite of receptive and expressive communication) and motor (composite of fine motor and gross motor). Scores are adjusted for prematurity, with a distribution centred on 100 with a standard deviation of 15. A 4-point change in cognitive score provides similar cognitive advantage as breast-feeding for at least 8 months and may be sufficient to obtain semi-skilled rather than unskilled work.⁴⁷ Expertise in Bayley-4 test administration is available within all Australian neonatal centres. A copy of the child's Bayley-4 results can be provided to parents upon request.

The trial will aim to conduct Bayley-4 assessments at 2 years cPNA. If participants are unable to undertake their Bayley-4 assessment at 2 years cPNA, a later Bayley-4 assessment will be undertaken as soon as reasonably possible and up to a maximum participant age of 3 years cPNA.

5.1.2 Secondary outcomes

Comprise short-term and longer-term neurodevelopmental and clinical outcomes as well as targeting physiological and molecular indicators of circadian rhythm development to inform mechanism and effectiveness of the intervention.

5.1.2.1 *Short term secondary outcomes*

- Survival to 36 w postmenstrual age (PMA)
- Weight, length, head circumference, and growth velocity (36 w PMA; 2 m, 6 m, 12 m cPNA)
 - Duration of hospitalisation
 - Tertiary hospital
 - Total duration of hospitalisation prior to first discharge home
- Severity of respiratory disease

•

- BPD (defined by the NICHD and shift of the oxyhaemoglobin dissociation curve),
- right shift of the SpO₂/P₁O₂ curve at 36 w PMA relative to the fetal oxyhaemoglobin dissociation curve
- duration of mechanical ventilation,
- duration any respiratory support
- days of oxygen supplementation
- Other neonatal morbidities including:
 - NEC stage II or more on Bell's classification
 - ROP stage II or stage III ROP, and presence of 'plus' disease or greater on ICROP3
 - Brain Grade 3 or 4 IVH, and presence of PVL
 - Sepsis defined as number of confirmed (blood culture positive) episodes of sepsis

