5.1.2.2 Long-term (2 y cPNA) secondary outcomes

- Survival
- Proportion of scores < 1 SD and < 2 SD below mean, for the primary cognitive sub-score outcome at 2 y cPNA
- Individual components of the Bayley-4 at approximately 2 y cPNA
- Neurobehaviour using the Infant Toddler Social-Emotional Assessment (ITSEA)⁵³
- Social communication using the Communication and Symbolic Behaviour Scales Infant-Toddler Checklist (CSBS-ITC) for early recognition of risk behaviours that may be predictive of later behavioural difficulties such as diagnosis of autism spectrum disorder
- Growth velocity
- Anthropometry including weight, height, BMI, fat-free mass
- Primary caregiver mental well-being
 - GAD-7
 - Center for Epidemiologic Studies Depression Scale Revised (CESD-R).
- 5.1.3 Circadian rhythm biological sub-study (KEMH only, n=~70): confirming intervention effect on rhythms
 - Time to onset, mesor, amplitude, and acrophase of circadian rhythms in temperature, heart rate, oxygen saturation, salivary melatonin and cortisol and/or urinary melatonin, and buccal cell clock gene expression at study entry, 7 d, 14 d, 28 d and then 4 weekly until discharge home.
- 5.1.4 Social Communication sub-study (n=infants identified at risk of ASD using the CSBS-ITC, in centres where ADOS-2 testing is available)
 - Assessment at 2 years corrected postnatal age with The Toddler Module of the Autism Diagnostic Observation Schedule - Second Edition (ADOS-2)⁵⁴. Two outcomes will be reported from the ADOS-2.
 - the continuous scores of the ADOS-2 (i.e., autism behavioural severity)
 - the dichotomous outcome of whether or not children exceed the 'ASD' threshold (to be defined).
- 5.1.5 Neonatal lung function and body composition sub-study (KEMH only, n=128)
 - Tidal volume
 - Respiratory rate
 - Area under the flow volume curve
 - Body volume
 - Body fat and fat free mass, and % body fat

5.1.6 Measurement of infant sleep quality and duration sub-study

- Parents will be asked to complete the Brief Infant Sleep Questionnaire (BISQ-R; 33 items) at 2 months and 6 months corrected postnatal age, to provide detail on their infants sleep behaviours over the previous 2 weeks.
- Parents will also be asked to keep a sleep diary of their own sleep behaviours over the same interval.

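### Section 10.6 lets extreme values be removed without limiting removal to errors, so genuine outcomes and, under some screens, the assigned scores of 49 could be dropped

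*Protocol*

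**What the plan says.** Protocol Section 10.6, whose heading covers missing, unused and spurious data, states: "Data will be reviewed prior to analysis for extreme outliers and where reasonable these data will be removed from the analyses". It gives no threshold, no list of variables and no named decision-maker for removal. It does not confine removal to errors and does not exempt any outcome.

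Section 10.1 plans the analysis "on an intention to treat basis" and "performed blinded to study group assignment". Children who cannot be tested on the Bayley-4 "due to death, disability, severe delay or performance below threshold for individual composite scores will be assigned a score of 49". The primary outcome "will be analysed using (1°) ttest and (2°) linear mixed effects regression".

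Section 5.1.1 describes the Bayley-4 scale "with a distribution centred on 100 with a standard deviation of 15". Section 5.1.2.2 makes low scores an outcome in themselves: "Proportion of scores < 1 SD and < 2 SD below mean". Section 5.1.2.1 lists durations of hospital stay, mechanical ventilation, respiratory support and oxygen among the secondary outcomes.

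**The concern.** The stated ground for removal is that a value is extreme, not that it is wrong. In this population extreme values are often real outcomes. An infant with severe lung disease can have a very long stay or long ventilation, and a child who died or is severely delayed is placed at 49 deliberately. Taking such values out of the analysis discards valid outcomes of randomised infants. That is hard to square with intention to treat and with the purpose of the 49 rule. It also affects the proportions below 1 SD and 2 SD, because those outcomes count exactly the values at risk.

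The primary test compares means, so tail values carry weight. If deaths or severe disability differ between arms, deleting them removes part of the treatment effect or hides part of a harm. It also narrows the apparent SD.

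**Working it through.** The protocol gives no figure for the outlier rule, so there is none to reproduce. The check asks whether 49 could be screened out, and what its removal would do.

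**Inputs.** Scale mean 100 and SD 15 (Section 5.1.1). Assigned score 49 (Section 10.1). Target difference 4 points (Section 10.2). The only cohort-level figure is in Section 3.1: "children born preterm perform at >0.8 SD below term peers on IQ tests". Carried over to the Bayley-4, which is an assumption, this gives a mean of about 100 − 0.8 × 15 = 88. A tested mean of 95 is a further assumption between the two. The shares of children at 49 are assumed throughout.

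**Step 1: distance of 49 from the mean.**
- Mean 100: (100 − 49)/15 = 3.4 SD
- Mean 95: (95 − 49)/15 = 3.07 SD
- Mean 88: (88 − 49)/15 = 2.6 SD

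**Step 2: common lower limits.** Tested children are taken as normal with mean m and SD 15, and a share f sits at 49.
- Pooled lower quartile: m + 15·z[(0.25 − f)/(1 − f)]. Pooled upper quartile: m + 15·z[(0.75 − f)/(1 − f)].
- Tukey fence: lower quartile − 1.5 × IQR.
- Pooled mean: (1 − f)m + 49f. Pooled variance: (1 − f)·225 + f(1 − f)(m − 49)².

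Example with m = 95 and f = 7%: the quartiles are 82.03 and 104.25, so the fence is 82.03 − 1.5 × 22.22 = 48.7.

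| Tested mean | Share at 49 | Tukey 1.5 × IQR | 3 SD limit | 2.5 SD limit | Screens that flag 49 |
|---|---|---|---|---|---|
| 100 | 0% | 59.5 | 55.0 | 62.5 | all three |
| 100 | 10% | 50.5 | 32.2 | 42.7 | Tukey only |
| 95 | 0% | 54.5 | 50.0 | 57.5 | all three |
| 95 | 6% | 49.7 | 37.7 | 46.8 | Tukey only |
| 95 | 7% | 48.7 | 35.9 | 45.2 | none |
| 88 | 0% | 47.5 | 43.0 | 50.5 | 2.5 SD only |
| 88 | 7% | 41.7 | 32.6 | 41.4 | none |

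The 0% rows are limits set without the 49s. The other rows are limits computed from data that contain them; the 49s widen the limits and can hide themselves. Whether 49 is flagged depends on a screen and a reference population that the protocol does not fix.

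**Step 3: effect of deleting the 49s (illustration only).** Tested mean 95, with 8% of controls and 6% of the intervention arm at 49.
- No difference among tested children: the planned difference is (0.08 − 0.06) × (95 − 49) = 0.02 × 46 = 0.92 points, and 0 after deletion. The shift of 0.92 is 0.92/4 = 23% of the target.
- Intervention children tested 4 points higher: the planned difference is 4 × 0.94 + 0.92 = 4.68, and 4 after deletion, a shift of 0.68.
- The same 4 points with the shares reversed: 4 × 0.92 − 0.92 = 2.76, and 4 after deletion, a shift of 1.24 that conceals harm.

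The SD within an arm, by the variance formula, is √330.8 = 18.2 at 6% and √362.7 = 19.0 at 8%. It falls to 15 after deletion.

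The pooled share in this illustration is 7%. At that share and a mean of 95, none of the three data-derived screens in the table flags 49. The illustration therefore supposes removal by judgement, or by fixed limits taken from the 100/15 norm (55 or 59.5).

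**The case against.** The heading of Section 10.6 refers to spurious data, removal is qualified by a test of reasonableness, and the next sentence speaks of samples. The clause may be aimed largely at laboratory and physiological measurements. Section 10.1 has a specific, mandatory rule for untestable children, and a general clean-up clause should not be read as cancelling it. Sections 5.3 and 10.1 keep the analysts blinded, and the review takes place before analysis. Detailed outlier criteria often sit in a SAP, which is not at hand. The phrase about extreme outliers could also mean the 3 × IQR convention, which gives 29.2 on the 100/15 scale and 24.2 at a mean of 95, so 49 would stay.

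Much of this stands. A reader might infer that the plan will delete the sickest infants, or that 49 would always be caught. The documents support neither. Removal is discretionary, it concerns data rather than infants, and the table shows plausible settings in which 49 is not flagged. Nor is there ground to suggest selective removal by arm, given the blinding.

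What remains is the wording. The sentence permits removal for extremeness, and neither the heading nor the 49 rule says which provision prevails. Blinding does not help where the share of extreme values itself differs between arms. Because the protocol grants the permission outright, this is a badly fixed rule and not merely detail left to a SAP.

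**Conclusion.** The point holds in a limited form. Section 10.6 allows valid extreme values to be removed, without restriction to errors and without exempting the primary outcome. That conflicts with intention to treat, with the purpose of the assigned 49s, and with secondary outcomes defined by low scores or long durations.

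Loss of the 49s is possible, not certain. It is likely under limits taken from the 100/15 norm. It is unlikely under 3 SD or Tukey limits if the cohort mean is about 88, or under data-derived limits if 7% or more sit at 49 with a tested mean of 95. The size of the bias is not known from the documents. About 0.9 points (0.7 to 1.2 in the variants shown) is an illustration resting on assumed shares of 6% and 8%, a tested mean of 95 and actual deletion of every 49. With equal shares and no difference among tested children there would be no shift. The sample size is not affected.

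**What to change.** Replace the outlier sentence in Section 10.6 with:

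> Values are corrected or set to missing only when source verification shows a recording or measurement error, decided while blinded to group. All verified values, including assigned scores of 49, are kept in the primary and secondary analyses. The influence of extreme values is examined in sensitivity analyses only.

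Rank-based or log-scale analyses of the durations would serve as such sensitivity analyses. The cost is a short text change in the protocol, carried into the SAP if one exists. It needs no extra infants, visits or data collection.
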